12.3.1 Equivalence test between Test Drug and reference product

Bioequivalence will be established for the primary endpoint (WOMAC® pain Score) if the 90% confidence interval for the test/reference ratio of mean change from baseline to week 4 is contained within [0.80, 1.25], using the per-protocol population.

The compound hypothesis to test is:

$$H_0: \mu_T / \mu_R \leq \theta_1 \text{ or } \mu_T / \mu_R \geq \theta_2 \text{ versus } H_A: \theta_1 < \mu_T / \mu_R < \theta_2$$

Where μ_T = mean of test treatment, and μ_R = mean of reference treatment.

H_0 will be rejected with a type I error $\alpha = 0.05$ (two 1-sided tests), if the 90% confidence interval for the ratio of means between test and reference products (μ_T / μ_R) is contained within the interval $[\theta_1, \theta_2]$, where $\theta_1 = 0.80$ and $\theta_2 = 1.25$.

Rejection of the null hypothesis H_0 supports the conclusion of equivalence of the two products.

12.3.2 Superiority test between Test Drug and placebo & superiority test between reference product and placebo

As a parameter for determining adequate study sensitivity, the Test Drug and RLD should both be statistically superior to placebo ($p < 0.05$, two-sided) for the primary endpoint (mean change from baseline), using the mITT study population and last observation carried forward (LOCF).

$$H_0: \mu_T \text{ or } \mu_R \geq \mu_{\text{Placebo}} \text{ versus } H_A: \mu_T \text{ or } \mu_R < \mu_{\text{Placebo}}$$

Where μ_T = mean of test treatment, and μ_R = mean of reference treatment.

H_0 will be rejected with a type I error $\alpha = 0.05$ (2-sided test). Rejection of the null hypothesis H_0 supports the conclusion of superiority to placebo. Analysis of covariance (ANCOVA) will be used to

compare Test Drug to placebo and RLD to placebo separately. The model will consist of treatment, investigator and baseline value as covariate. Post hoc test comparison will be made to detect the group difference.

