#### **5. HYPOTHESES TESTING**

##### **Hypothesis of Equivalence (Primary Endpoint)**

The null hypothesis to be tested is that the ratio of mean change from baseline in WOMAC Likert pain score between test and reference drug is less than or equal to 0.80 or greater than or equal to 1.25 vs the alternative hypothesis that this ratio is within the interval from 0.80 to 1.25:

$H_0: \mu_T / \mu_R \leq \theta_1$  or  $\mu_T / \mu_R \geq \theta_2$  versus  $H_A: \theta_1 < \mu_T / \mu_R < \theta_2$

Where  $\mu_T$  = mean of test treatment, and  $\mu_R$  = mean of reference treatment

Typically,  $H_0$  will be rejected with a type I error  $\alpha = 0.05$  (two 1-sided tests), if the 90% confidence interval for the ratio of means between test and reference products ( $\mu_T / \mu_R$ ) is contained within the interval  $[\theta_1, \theta_2]$ , where  $\theta_1 = 0.80$  and  $\theta_2 = 1.25$ .

A two-sided, 90% confidence interval on the test/reference ratio for mean change from baseline to Week 4 in total WOMAC Pain Subscale score for the Target Knee will be constructed using Fieller's method. The estimates of treatment means and standard errors will be obtained from Analysis of Covariance (ANCOVA) of the Test and Reference results, using a statistical model containing fixed effects for treatment and center and baseline WOMAC Pain Subscale score as covariate.

Bioequivalence will be established if the 90% confidence interval for the ratio of test/reference means is contained within the interval  $[0.80, 1.25]$  for Per Protocol population.

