### **Hypothesis of Superiority (Primary Endpoint)**

The null hypothesis to be tested is that there is no difference in the mean change from baseline to Week 4 in total WOMAC Pain Subscale score for the Target Knee between the active treatment and the Placebo treatment vs the alternative hypothesis that the reduction in the WOMAC Pain Subscale score is greater for both active treatments than for placebo:

$H_0: \mu_T = \mu_P$  and  $\mu_R = \mu_P$  versus  $H_A: \mu_T < \mu_P$  and  $\mu_R < \mu_P$

Where  $\mu_T$  = mean of test treatment,  $\mu_R$  = mean of reference treatment,  $\mu_P$  = mean of Placebo treatment.

The hypothesis testing will be performed separately for the Test treatment versus the Placebo treatment and for the Reference treatment versus the Placebo treatment using Analysis of Covariance (ANCOVA) with a statistical model containing fixed effects for treatment and center and baseline WOMAC Pain Subscale score as covariate.

Superiority will be established if the mean change from baseline for each active treatment is less than, and statistically significantly different from ( $p < 0.05$ ), that for the Placebo using the

modified intent-to-treat (mITT) population and with Last Observation Carried Forward (LOCF) approach.

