### **7.1.2 Adjustment for multiplicity**

The study will test three hypotheses:

1. Equivalence of the Test and Reference treatments
2. Superiority of Test to Placebo treatment
3. Superiority of Reference to Placebo treatment

Possible inflation of Type I error rate will be controlled by declaring the study a success only if all 3 hypotheses are simultaneously true. Therefore there will be no need to apply any multiplicity adjustment methods.

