#### **7.11.2.1 Analysis of clinical equivalence of test and reference treatments**

To show the clinical equivalence, estimates of LS mean change from baseline to Week 4 in the WOMAC Pain Subscale score will be calculated for the test and reference treatment, and then the 90% CI for the LS mean ratio will be constructed using Fieller's method. Bioequivalence will be established if the 90% confidence interval for the ratio of test/reference LS means is contained within the interval [0.80, 1.25].

To this end, first an ANCOVA model will be fit with change from baseline to Week 4 in the WOMAC Pain Subscale score as outcome, baseline WOMAC Pain Subscale score as covariate and treatment, center and treatment-by-center interaction as factors on the data from test and reference treatments only (excluding Placebo subjects):

$$Y_{ijk} = b + a \cdot B_{ijk} + T_i + C_j + TCI_{ij} + \varepsilon_{ijk}$$

Where

- $Y_{ijk}$  is the change from baseline to Week 4 in WOMAC Pain Subscale score for the  $k$ th subject in the  $j$ th center with  $i$ th treatment
- $b$  is model intercept
- $B_{ijk}$  is the baseline WOMAC Pain Subscale score for the  $k$ th subject in the  $j$ th center with  $i$ th treatment
- $a$  is the model parameter associated with baseline WOMAC Pain Subscale score
- $T_i$  is the effect of the  $i$ th treatment
- $C_j$  is the effect of the  $j$ th center
- $TCI_{ij}$  is the interaction effect of the  $i$ th treatment and the  $j$ th center
- $\varepsilon_{ijk}$  is the random error (normally distributed with zero expected value)

If the treatment-by-center interaction factor is not significant at the 0.05 level, the model will be rerun without the interaction term. Treatment LS means and standard errors will be estimated from this model. Then Fieller's formula will be applied; covariance between treatment means will be assumed to be 0. See [appendix 11.2](#) for complete description of Fieller's formula.

Equivalence will be illustrated graphically by a plot including a vertical line corresponding to the 90% CI around the Test/Reference ratio with the ratio itself indicated by a dot with reference lines for 80% and 125%.

Analysis of bioequivalence will be performed primarily on the Per Protocol population, and additionally on the ITT and mITT populations as a sensitivity analysis.

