### 7.11.2.2 Analysis of superiority to placebo control

The analysis of superiority will be performed for the primary endpoint separately for the Test treatment versus the Placebo treatment and for the Reference treatment versus the Placebo treatment. Each of these analyses will be performed using an ANCOVA model with change from baseline to Week 4 in the WOMAC Pain Subscale score as outcome, baseline WOMAC Pain Subscale score as covariate and treatment, center and treatment-by-center interaction as factors (mathematical statement of this model is the same as for the equivalence model). If the treatment-by-center interaction factor is not significant at the 0.05 level, the model will be rerun without the interaction term. The model will be fit on data from the Test and Placebo treatment

for analysis of superiority of the Test treatment and separately on data from the Reference and Placebo treatment for analysis of superiority of the Reference treatment. From this model, the least square (LS) mean estimate for each treatment group with the 95% CI will be calculated; further, an estimate of the LS mean difference between the active treatment (Test or Reference) and Placebo with 95% CI and the p-value for test of no difference will be calculated.

Superiority will be established if the mean change from baseline to Week 4 for each active treatment is estimated to be less than, and statistically significantly different from ( $p < 0.05$  for test of no difference) that for the Placebo.

Superiority will be illustrated graphically by a plot including two vertical lines (for Test drug vs. Placebo and Reference Drug vs. Placebo) corresponding to the 95% CI around the Active – Placebo difference with the difference itself indicated by a dot with reference line for 0 difference.

Analysis of superiority will be performed primarily using the mITT population, and additionally on the ITT and PP populations as a sensitivity analysis.

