## **8. CHANGES FROM PROTOCOL-SPECIFIED ANALYSES**

There are no changes from the protocol-specified analyses.

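### The SAP gives two primary models for the three deciding tests: a fixed main-effects ANCOVA in section 5 and an interaction pre-test in 7.11.2

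*SAP*

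**What the plan says.** SAP 5 states the model for equivalence, "using a statistical model containing fixed effects for treatment and center and baseline WOMAC Pain Subscale score as covariate", and repeats it for the two superiority tests, "with a statistical model containing fixed effects for treatment and center and baseline WOMAC Pain Subscale score as covariate". It mentions neither an interaction nor a preliminary test.

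Protocol 12.3.2 gives the matching superiority model: "The model will consist of treatment, investigator and baseline value as covariate". Protocol 12.3.1 names no model for the equivalence interval.

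SAP 7.11.2.1 fits Test and Reference data with a treatment-by-center term added, then applies this rule: "If the treatment-by-center interaction factor is not significant at the 0.05 level, the model will be rerun without the interaction term". SAP 7.11.2.2 repeats the rule for each active arm against placebo and says that the "mathematical statement of this model is the same as for the equivalence model".

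SAP 7.1.2 controls error by "declaring the study a success only if all 3 hypotheses are simultaneously true". SAP 8 states: "There are no changes from the protocol-specified analyses".

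**The concern.** When a pre-test is not significant, 7.11.2 falls back to the SAP 5 model and the sections agree. When it is significant, they give different point estimates, standard errors and p-values for the same primary test. Both results could be called pre-specified, because no passage ranks the sections.

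The decision is taken three times, on overlapping data sets, so the three tests that must all succeed can rest on different models. A retained interaction also changes what is estimated. The treatment effect becomes an average over centers that depends on the center weights in the LS means, and the available text does not state them. Small centers can then count as much as large ones: SAP 7.11.1 accepts a pooled center with 10 Per Protocol patients and as few as one in an arm.

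At stake are an unambiguous primary result and some precision. Control of type I error is not at stake.

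**Working it through.** **1. The texts side by side.**

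| Test | Protocol | SAP 5 | SAP 7.11.2 |
|---|---|---|---|
| Test/Reference equivalence | no model named | treatment, center, baseline | adds treatment-by-center; drops it if p ≥ 0.05 |
| Test vs placebo | treatment, investigator, baseline | treatment, center, baseline | same pre-test, own data set |
| Reference vs placebo | treatment, investigator, baseline | treatment, center, baseline | same pre-test, own data set |

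The statement in SAP 8 is therefore wrong for the two superiority tests. For equivalence the conflict lies within the SAP.

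**2. The plan's own figures.** The inputs are from SAP 3.2: mean reductions 5.85 (SD 4.23) on active and 4.68 (SD 4.89) on placebo, a difference of 1.17.
- Superiority: n = 2(1.960 + 1.282)² × 4.89² / 1.17² ≈ 368 per arm, within 3% of the stated 363.
- Equivalence: two one-sided tests on the log scale, with σ² = ln(1 + 0.75²) and ratio 0.95, give 261 exactly.
- Dropout: 363 / 0.90 rounds up to 404, and 3 × 404 = 1212.

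This point disputes none of these figures.

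**3. How often the sections part.** With no true interaction each pre-test fires 5% of the time. If the three were independent, the chance of at least one would be 1 − 0.95³ = 14.3%. They share arms, so it is a little lower: 12.5-13.2% in 20,000 simulated trials for each of 10, 30 and 60 equal centers. In 12.4-13.1% of trials the three tests end up on different models.

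**4. What a retained interaction does to precision.** Assume equal center weights in the LS means and equal arms of size n_j in center j, for K centers.
- Interaction model: Var = (2σ²/K) × mean(1/n_j).
- Main effects: Var = 2σ² / (K × mean(n_j)).
- SE ratio = √[mean(n_j) × mean(1/n_j)], which is 1 for equal centers. For lognormal sizes with log-SD s it is exp(s²/2).

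Before pooling this gives 1.08 at s = 0.4, 1.38 at 0.8 and 1.65 at 1.0. Pooling small centers pulls the larger values down, as the simulation in step 5 shows.

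**5. Effect on study success.** The simulation used 3,000 three-arm trials per setting, with 363 patients per arm, the SAP 3.2 means and SDs, and a true Test/Reference ratio of 1. Assumed values were 20 or 30 centers, pooling to at least 10 patients, blocks of 3 within center, baseline-change correlation 0.3, center SD 0.5 and the same patients for all tests. Monte Carlo error is about 0.3 points on paired differences. Each cell shows 20 centers; 30 centers.

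| Log-SD of center size | SE ratio, Test − placebo | SE ratio, Fieller with covariance 0 | Power for all three: main effects vs SAP 7 |
|---|---|---|---|
| 0 | 1.00; 1.00 | 1.00; 1.00 | 0.902 vs 0.902; 0.900 vs 0.900 |
| 0.4 | 1.08; 1.08 | 1.04; 1.04 | 0.909 vs 0.905; 0.920 vs 0.914 |
| 0.8 | 1.28; 1.24 | 1.11; 1.10 | 0.900 vs 0.873; 0.906 vs 0.890 |
| 1.0 | 1.38; 1.32 | 1.15; 1.13 | 0.894 vs 0.863; 0.896 vs 0.875 |

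At least one pre-test fired in 12.3-13.7% of trials. The all-three verdict differed between the two sections in 0.03% of trials (log-SD 0), 0.6-0.7% (0.4) and 1.8-3.2% (0.8-1.0). Dividing by the firing rate, a firing pre-test changes the verdict about 4-6% of the time at log-SD 0.4 and 13-26% at 0.8-1.0. Repeating the simulation independently gave SE ratios of 1.00, 1.08 and 1.23-1.36, and verdict changes of 0%, 0.4% and 1.5-3.3%.

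**6. Type I error.** For Test vs placebo, two-sided rejection under the null was 0.049-0.050 with the SAP 7 rule and 0.046-0.047 with main effects.

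**7. If effects truly differ by center.** With an assumed interaction SD of 1.0 point, 10 to 60 centers and no baseline covariate in the simulation, pre-tests were significant in 13-74% of trials. Power for a single superiority test was 0.860-0.945 under the rule and 0.919-0.957 under main effects.

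**The case against.** The strongest reply is that SAP 5 states hypotheses and SAP 7.11.2 supplies the method. The usual outcome of the rule is exactly the SAP 5 model, and Protocol 12 leaves statistical detail to the SAP. The rule is automatic and fixed in advance, and it does not inflate type I error. The 12-14% counts model switches, not changed verdicts; with equal centers only about one firing in 400 changes the verdict. The larger effects need very unequal centers and equal LS-mean weights, neither of which is in the documents. The weights may be set in Appendix 11.2 (code fragments), which is missing from the available text. Correcting SAP 5 and SAP 8 would remove the contradiction without dropping the pre-test.

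Most of this stands as a limit on size. There is no validity failure, the average cost is small, and the weights cannot be called absent from the plan. It does not remove the conflict. Elaboration adds detail to a stated model, whereas here 7.11.2 can replace that model with another that yields a different interval and p-value. Even on this reading, SAP 5 and SAP 8 are wrong as written.

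**Conclusion.** The concern holds. SAP 5 and SAP 7.11.2 prescribe different primary models whenever a treatment-by-center test is significant, and SAP 8 is inaccurate for both superiority tests. With no true interaction, about one trial in eight would meet the conflict in at least one of the three tests, a figure that barely depends on the center assumptions.

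The consequences do depend on them. With equal center weights and 20-30 centers, the loss of power for passing all three tests is nil for equal centers, about half a point at log-SD 0.4 and 1.6-3.1 points at 0.8-1.0. Per-test losses are at most 1.6 points. The plan should be corrected, but the trial's validity is not in doubt.

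**What to change.** - In SAP 7.11.2.1 and 7.11.2.2, name the ANCOVA with treatment, pooled center and baseline as the only primary model for all three tests, whatever the interaction p-value. Delete the conditional refit. SAP 7.11.3 analyzes its WOMAC and POM endpoints like the primary one, so it would follow.
- Report the treatment-by-center test and per-center estimates as a separate consistency check.
- State the center weights behind the LS means, unless Appendix 11.2 already does. They matter for the Fieller ratio even under main effects.
- If the sponsor prefers to keep the pre-test, correct SAP 5 and list the superiority change in SAP 8.

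This is SAP wording only, with no new data or patients, and is best done before the database lock that precedes planned unblinding. The cost is interpretive: if effects differ by center, the headline difference is a precision-weighted average whose SE ignores center-to-center variation, so it is too small for inference beyond these centers. The fixed-effect interaction model shares that limit.

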### **3.2.1 Equivalence between test and reference product**

At least 261 subjects in Test Drug and 261 subjects in Reference Drug group will be required to show bioequivalence between Test and Reference product with 90% power and 5% level of significance assuming the following estimates:

- 1) 5% difference between Test and Reference of mean change in WOMAC score
- 2) 75 % inter subject coefficient of variation for Reference in WOMAC Score
- 3) Equivalence margin of 80.00-125.00%

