### **7.11.1 Center pooling**

To eliminate potential effect of random fluctuations at small center on the efficacy endpoints small centers will be pooled. A study center will be pooled if it doesn't meet both of the following conditions:

- It has at least 10 patients in the Per Protocol population;
- It has at least one patient in each treatment group in the Per Protocol population.

The smallest center that does not meet the above requirements will be pooled with the next smallest center. The procedure will be repeated until all pooled centers meet the above two requirements.

Pooled center will be used in all efficacy analyses.

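### The primary Fieller interval forces the covariance of the Test and Reference LS means to zero, although both come from one ANCOVA with shared center effects; when centers differ in size the 90% CI is too wide and equivalence power is lost

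*SAP*

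**What the plan says.** SAP 7.11.2.1 makes the bioequivalence decision on a Fieller interval: "the 90% CI for the LS mean ratio will be constructed using" that method, and it must lie within 0.80 to 1.25. The model is fitted to Test and Reference subjects together, with "baseline WOMAC Pain Subscale score as covariate and treatment, center and treatment-by-center interaction as factors". If the interaction is not significant at 0.05, "the model will be rerun without the interaction term". The section then says "Treatment LS means and standard errors will be estimated from this model" and adds that "covariance between treatment means will be assumed to be 0". It gives no reason for that last rule.

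SAP section 5 describes the same analysis directly in its main-effects form, "using a statistical model containing fixed effects for treatment and center and baseline WOMAC Pain Subscale score as covariate". The additive model is therefore the expected final model.

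SAP 7.11.1 pools small centers. One of its two conditions for leaving a center unpooled is "It has at least 10 patients in the Per Protocol population"; the other is at least one patient in each arm. It sets no upper limit on center size. The SAP text reviewed does not say whether LS means weight centers equally or by observed size.

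**The concern.** Two arm means are independent when each is computed only from its own arm. LS means from an additive ANCOVA are not. Each is the average of the estimated center effects plus or minus a treatment term, and the center effects are estimated from both arms together. The shared part raises the standard error of each LS mean. It should then largely cancel in the contrast Test − θ × Reference on which Fieller's interval rests. With the covariance set to zero it cannot cancel.

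This interval is one of three tests that must all succeed (SAP 7.1.2), so an avoidable loss of precision can make a truly equivalent product fail. The superiority tests in SAP 7.11.2.2 are not affected, because they take the LS mean difference and its CI straight from the model.

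**Working it through.** **Inputs.** Mean reduction 5.85 and SD 4.23 in both active arms (SAP 3.2). True ratio 0.95, CV 75%, limits 0.80–1.25, and 261 per arm for equivalence (SAP 3.2.1). 363 evaluable per arm, 10% dropout, 404 randomized per arm (SAP 3.2.2). Pooling floor of 10 per-protocol patients over three arms (SAP 7.11.1). Center numbers and sizes are not in the documents, so the layouts below are assumptions.

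**The plan's own figures.** A parallel-group two one-sided test on the log scale, with σ² = ln(1 + 0.75²) and ratio 0.95, reaches 90% power at 261 per arm. This matches the SAP. 363 / 0.90 = 403.3, rounded up to 404, also matches. However, the planned analysis is Fieller on untransformed means. With the same inputs that test needs about 354 per arm, and 261 gives about 80% power. At 363 per arm power is about 91%, so there is little to spare above 90%.

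**Covariance of the LS means.** Take the additive model with J centers, n_j subjects per arm in center j, N per arm, equal center weights, and the baseline term ignored. Let M be the equally weighted average of the center means and d the treatment difference. The LS means are M ± d/2, and M and d are uncorrelated, so:

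- variance of each LS mean: v = (σ²/2)[(1/J²)Σ(1/n_j) + 1/N]
- covariance: c = (σ²/2)[(1/J²)Σ(1/n_j) − 1/N]

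The covariance is never negative, and it is zero only when all n_j are equal.

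**Effect on Fieller.** The variance of Test − θ × Reference is v(1 + θ²) − 2θc. Setting c = 0 overstates it. With correlation ρ = c/v and θ near 1, the interval is too wide by a factor of about 1/√(1 − ρ).

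**One layout in full.** Five centers of 50 per arm and twenty of 5 per arm, so J = 25 and N = 350.

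- Σ(1/n_j) = 5/50 + 20/5 = 4.1, and 4.1/625 = 0.00656; 1/N = 0.00286; σ² = 4.23² = 17.89
- v = 8.946 × (0.00656 + 0.00286) = 0.0842
- c = 8.946 × (0.00656 − 0.00286) = 0.0331
- ρ = 0.0331/0.0842 = 0.39; width factor 1/√0.61 = 1.28
- Type I error at θ = 0.80: 1.645 × √[1.64/(1.64 − 1.6 × 0.39)] = 2.09, a one-sided tail of about 0.018

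**Across layouts.** The intervals use the exact LS-mean covariance matrix, including baseline, at an observed ratio of 1.00. Type I error is at ratio 0.80 and power at ratio 0.95, with SD 4.23.

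| Layout (active arms) | ρ | CI, covariance 0 | CI, model covariance | Too wide by | Type I error, covariance 0 | Power, covariance 0 vs model |
|---|---|---|---|---|---|---|
| 20 equal centers, 18 per arm | 0.00 | 0.915–1.093 | 0.915–1.093 | 0% | 0.050 | 0.923 vs 0.923 |
| 20 centers, sizes 1:5 | 0.12 | 0.910–1.099 | 0.915–1.093 | 6% | 0.040 | 0.909 vs 0.924 |
| 30 centers, sizes 1:10 | 0.22 | 0.905–1.105 | 0.915–1.092 | 13% | 0.031 | 0.890 vs 0.925 |
| 5 of 50 plus 20 of 5 per arm | 0.39 | 0.890–1.123 | 0.913–1.095 | 28% | 0.018 | 0.816 vs 0.914 |
| 3 of 100 plus 20 of 3 per arm | 0.64 | 0.862–1.160 | 0.915–1.093 | 67% | 0.004 | 0.610 vs 0.914 |

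With the model covariance, type I error is 0.050 in every layout. The last row is a bound: a center with 3 in each active arm reaches the pooling floor only if it has 4 on placebo. At the SAP's CV of 75%, power falls from 0.908 to 0.867 (1:10), from 0.895 to 0.784 (5 plus 20) and from 0.895 to 0.559 (extreme). The baseline covariate contributes a correlation between 0 and −0.01, so the center term drives the effect.

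**The case against.** The strongest objection is that the effect is conditional. The correlation is essentially zero in three situations: equal center sizes, LS means weighted by observed center sizes, and a retained treatment-by-center interaction. SAP 7.11.2.1 refers to appendix 11.2 for the formula. That appendix is not in the text reviewed, and it might specify observed-size weights, in which case assuming zero would be nearly exact.

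The error is also conservative, so it is a cost to the sponsor and not a risk of approving a non-equivalent product. It may be small: with lognormal center sizes, the pooling floor applied and a size CV of 0.4, the interval is about 4% too wide and power goes from 92.5% to 91.5%. At a size CV of 0.6 the excess is 7–8% and power about 90.4–90.8%. At 1.0 it is 11–16% and power 88–89.5%.

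The conditions and the direction stand, and they limit how serious the point is. They do not rescue the rule. It is written in the body of the SAP without a reason and without the weighting that could justify it. The expected final model is the one in which it fails, and nothing in the plan makes center sizes equal.

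**Conclusion.** The point holds. Under the additive model with equally weighted centers, the zero-covariance rule is wrong whenever pooled centers differ in size, and it makes the primary 90% CI too wide. In the moderate layouts tabulated the excess is 6% to 28%; milder inequality gives about 4%, and an extreme layout gives 67%. Type I error stays at or below 5%. The loss is in power, from about one percentage point to about ten in the moderate layouts at SD 4.23. Because the planned Fieller test starts at only about 91% power under the SAP's 75% CV, a loss of even two points takes it below the 90% target.

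These figures rest on assumed center layouts, about 350 to 370 per-protocol subjects per active arm, and equal center weights. This should be corrected, but it does not threaten the validity of a positive equivalence finding.

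**What to change.** In SAP 7.11.2.1, replace the zero-covariance rule with: *The covariance of the Test and Reference LS means will be taken from the same fitted ANCOVA and used in Fieller's formula.* An equivalent form is to test LSmean(T) − 0.80 × LSmean(R) and LSmean(T) − 1.25 × LSmean(R) as contrasts within the model. State the center weights used for LS means, and bring appendix 11.2 into line.

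Observed-size weights are an alternative that makes the covariance close to zero, but they change how the means are averaged over centers, so they should be chosen deliberately. Use one rule for all Test/Reference ratios (mITT and ITT sensitivity analyses, secondary endpoints, subgroups and forest plot) for consistency, although only the primary interval carries the decision.

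The cost is one SAP sentence and one program option, made before unblinding. Where the covariance is truly zero, the result does not change.
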